5.4.2. Main Analytical Approach

For the secondary effectiveness endpoint of change from baseline in FACE-Q Satisfaction with Skin overall converted score at Month 1, a 2-sided 2-sample t-test, if the normality assumption holds, otherwise, the Wilcoxon rank-sum test will be used to compare mean change from baseline values between treatment and control groups using the mITT population.

For the secondary effectiveness endpoint of AFLS responder status at Month 1, the 95% CI will be provided for the proportion of responders for each treatment group. For comparison of treatment group versus control group at Month 1, the responder rate difference, 95% CI for the risk difference and p-value will be estimated based on Fisher's exact test using the mITT population with baseline AFLS score of 2 on both cheeks or 3 on both cheeks.

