6.1 Inclusion Criteria

Subjects are eligible to be included in the study only if all of the following criteria apply:

1. Age 22 or over and in good general health
2. Has an ACSS score of 2 for both cheeks or 3 for both cheeks on the 5-point Allergan Cheek Smoothness photonumeric scale (range: 0 to 4), as judged live by the Evaluator (Fitzpatrick V/VI safety cohort)
3. Has a FACE-Q Satisfaction with Skin Questionnaire sum score of 39 or less (sum score of 39 is equivalent to Rasch-transformed score of 69) unless enrolled as part of the Fitzpatrick V/VI safety cohort
4. Ability to follow study instructions and likely to complete all required visits
5. Written informed consent and data privacy consent have been obtained

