7.4 Method of Treatment Assignment and Allocation Ratio

Prior to initiation of study treatment, each consented subject will be assigned a subject number that will be recorded on the appropriate eCRF. At the time of randomization (ie, at the Randomization/Initial Treatment visit), eligible subjects will be randomly assigned at a 2:1 ratio to treatment group or control group. Randomization will be within each study site. All subjects will be centrally randomized using an IWRS. Before the study is initiated, the log-in information and directions for the IWRS will be provided to each site. If subjects are withdrawn, they will not be replaced.

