10.3.1.3 Secondary Endpoint Analysis

The first secondary effectiveness variable is subject responses on the FACE-Q Satisfaction with Skin questionnaire. The responses to the 12 items will be summed and converted to a scale score that ranges from 0 to 100 (higher score indicates more satisfaction) using the algorithm developed by the FACE-Q scale developers. The secondary effectiveness analysis is mean change from baseline in FACE-Q scale score at Month 1.

The other secondary effectiveness variable is the EI's assessment of fine lines on the cheeks on the AFLS. The AFLS responder rate at Month 1 will be analyzed in the same manner as the ACSS responder rate. Only subjects with baseline AFLS score of 2 on both cheeks or 3 on both cheeks will be included in the analysis.

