The primary effectiveness variable is the cheek skin smoothness based on the ACSS evaluated by EIs. The primary effectiveness endpoint is the ACSS responders at Month 1 defined as a participant who achieves at least a 1-point improvement from baseline on both cheeks based on ACSS. Month 1 refers to 1 month after the preceding treatment (initial or touch-up) for participants in the JUVÉDERM VOLITE XC treatment group or 1 month after randomization for participants in the no-treatment control group.

The null hypothesis is that there is no difference between the JUVÉDERM VOLITE XC treatment group and the no-treatment control group in the ACSS responder rate at Month 1. The alternative hypothesis is that there is difference between the JUVÉDERM VOLITE XC treatment group and the no-treatment control group in the ACSS responder rate at Month 1. These hypotheses are stated as:

$$H_0: P_v - P_c = 0$$

$$H_a: P_v - P_c > 0 \text{ or } P_v - P_c < 0$$

where P_v and P_c denote the responder rates for the JUVÉDERM VOLITE XC group at Month 1 after the preceding treatment (initial or touch-up) and for the no-treatment control group at Month 1 after randomization, respectively. The treatment effects between JUVÉDERM VOLITE XC and the no-treatment control group will be compared using the statistical method described in [Section 5.3.2](#). If the 2-sided p-value is less than 0.05 and the responder rate is greater for JUVÉDERM VOLITE XC than for the no-treatment control group, then JUVÉDERM VOLITE XC will be considered superior to the no-treatment control group.

3. Sample Size Determination

A sample size of 112 participants in the treatment group and 56 participants in the control group will provide 99.9% power to detect a difference of at least 40% in the responder rates on the ACSS between the groups, based on a 2-sided Fisher's exact test at the 5% level. The treatment group is assumed to have at least an 80% responder rate at Month 1, and the control group is assumed to have at most a 40% responder rate. The assumptions of responder rates are estimated from Allergan Study V12-001. Accounting for participant attrition of 20% during the study, 210 participants will be randomized at a 2:1 ratio to treatment group and control group. Randomization will occur within each study site.

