5.4. Secondary Effectiveness Endpoints Analysis

5.4.1. Secondary Effectiveness Endpoints

The secondary effectiveness endpoints are change from baseline in FACE-Q Satisfaction with Skin overall converted score at Month 1 during the CP and AFLS responder at Month 1 during the CP.

Each participant's responses to the 12 items on the FACE-Q Satisfaction with Skin questionnaire will be summed and converted to a scale score that ranges from 0 to 100 (higher score indicates more satisfaction) using the algorithm developed by the FACE-Q scale developers (see [Sections 6.5.1](#) and [6.5.2](#) for details of derivation). The mean change from baseline in FACE-Q overall converted score at Month 1 will be calculated. The change from baseline value will be computed as the value for the postbaseline visit minus the baseline value. The analysis will be conducted using observed data (eg, no imputation for missing baseline or Month 1 FACE-Q scale scores).

An AFLS responder is defined as participant who achieves at least 1-point improvement from baseline on the AFLS scale (see Table 5-3) on both cheeks.

Table 5-3 **Allergan Fine Lines Scale**

Score	Grade	Description
0	None	No fine lines
1	Minimal	1-2 superficial lines
2	Moderate	3-5 superficial lines
3	Severe	Greater than 5 superficial lines; no crosshatching
4	Diffuse	Diffuse superficial lines; crosshatching

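### The FACE-Q secondary test switches between a t-test and a Wilcoxon test on an undefined normality check and ignores baseline; one prespecified ANCOVA would be a free improvement

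*SAP*

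**What the plan says.** SAP 5.4.2 compares the arms on FACE-Q change at Month 1 in the mITT population by "a 2-sided 2-sample t-test, if the normality assumption holds, otherwise, the Wilcoxon rank-sum test will be used to compare mean change from baseline values". It gives no test, threshold or unit of checking (each arm, pooled changes or residuals) for normality. SAP Section 1 places table specifications in a separate document, which was not available.

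The quantity of interest is a mean in both documents. SAP 5.4.1 states "The mean change from baseline in FACE-Q overall converted score at Month 1 will be calculated", and Protocol 10.3.1.3 states "The secondary effectiveness analysis is mean change from baseline in FACE-Q scale score at Month 1". The protocol names no between-group test or covariate.

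Missing scores are not filled in: "The analysis will be conducted using observed data (eg, no imputation for missing baseline or Month 1 FACE-Q scale scores".

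For the other secondary endpoint, AFLS, SAP 5.4.2 says "the responder rate difference, 95% CI for the risk difference and p-value will be estimated". FACE-Q has no matching statement. In SAP Table 5-4 the row for the FACE-Q Satisfaction with Skin converted score covers the treated and repeat-treatment periods only, not the control period in which this endpoint sits.

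**The concern.** Four features are open to question.

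1. **Undefined switch.** The test depends on a check that the SAP does not specify. SAP 5.1 places the analysis after database lock and release of the randomization schedule, so the choice would be made with assignments known.
2. **Moving target.** A rank-sum test concerns the probability that a treated subject's change exceeds a control subject's. It matches a mean comparison only if treatment shifts every subject equally.
3. **No between-group estimate.** The p-value comes with no stated difference and interval.
4. **Baseline used only by subtraction.** A change score on observed data requires a baseline value, so every analysed subject has one and adjusting for it would lose nobody.

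At stake are the clarity and precision of the first secondary endpoint. The primary analysis is not affected.

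**Working it through.** **The plan's own figures.** None exists for FACE-Q. The stated sample-size figures reproduce: ACSS Fisher power at 112/56, 80% v 40%, is 99.91% (stated 99.9%); AFLS at 72/36, 80% v 45%, is 94.40% (stated 94.4%); 168/(1 − 0.20) = 210.

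**Inputs.** From the documents:
- 2:1 allocation and a two-sided 5% level.
- An entry cap, "Has a FACE-Q Satisfaction with Skin Questionnaire sum score of 39 or less" (converted score 69, Protocol 6.1).
- Month 1 N between 112/56 and 140/70. SAP Section 3 has "Accounting for participant attrition of 20% during the study", so losses by Month 1 should be smaller than 20%; 140/70 is all 210 randomised, the upper bound.

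Assumed, because the documents give none: Month 1 SD 17; baseline–Month 1 correlation ρ of 0.3, 0.5 or 0.7; effects of 0, 8 or 12 points.

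**Precision, by formula.** Let k be baseline SD divided by Month 1 SD. Change-score variance is proportional to 1 + k² − 2kρ, and ANCOVA variance to 1 − ρ².
- k = 1: the ratio is (1 + ρ)/2 = 0.65, 0.75, 0.85.
- k = 0.5: 0.91/0.95 = 0.96; 0.75/0.75 = 1.00; 0.51/0.55 = 0.93.

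**Precision, by simulation** (2,000 trials per scenario, capped baseline, rounded scores, Month 1 clipped to 0–100, HC3 standard errors, no site terms). Variance ratio, ANCOVA to change score, at 112/56:

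| Baseline setting | ρ 0.3 | ρ 0.5 | ρ 0.7 |
|---|---|---|---|
| Latent mean 45 | 0.73 | 0.81 | 0.87 |
| Latent mean 60 | 0.77 | 0.87 | 0.93 |
| Baseline SD half of Month 1 SD | 0.97 | 1.01 | 0.94 |

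The first row follows from the empirical SDs of the effect: (2.62/3.06)² = 0.73, (2.44/2.72)² = 0.81, (2.02/2.17)² = 0.87. The cap narrows the baseline spread, which generally brings the ratios nearer 1 than the k = 1 formula gives.

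Power for 8 points, t-test v ANCOVA:

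| Setting | ρ 0.3 | ρ 0.5 | ρ 0.7 |
|---|---|---|---|
| Mean 45, 112/56 | 74 v 86% | 84 v 90% | 97 v 98% |
| Mean 45, 140/70 | 79 v 90% | 92 v 95% | 99 v 99% |
| Half-SD baseline, 112/56 | 84 v 85% | 92 v 91% | 97 v 98% |

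At 12 points both exceed 97% in every scenario.

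**Target quantity.** Take control change as normal, mean 2, SD 15. The SD of a difference between two subjects is 15√2 = 21.2.
- Uniform 8-point shift: P(treated > control) = Φ(8/21.2) = 0.65. Power at 112/56 is 90% for the t-test and 88% for Wilcoxon.
- 25% of subjects gain 32 points and the rest gain none: the mean gain is 0.25 × 32 = 8, but P = 0.75 × 0.5 + 0.25 × Φ(32/21.2) = 0.61. Power at 112/56 is 75% v 64%.

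The same mean effect therefore gives a different rank quantity. With Shapiro-Wilk at 0.05 as an assumed check, the second case goes to Wilcoxon in 31% of trials at 112/56. The two-stage rule itself has about 71% power there, between the two pure analyses. At 140/70 the figures are about 85% (t-test), 73–75% (Wilcoxon) and 80% (two-stage).

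**Validity.** Over the 18 null scenarios (Monte Carlo SE about 0.5 points), type I error was:

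| Analysis | Type I error |
|---|---|
| t-test | 4.4–6.0% |
| Wilcoxon | 4.6–5.9% |
| Two-stage, assumed check | 4.4–6.0% |
| ANCOVA | 3.8–5.6% |

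A separate run with identical normal, skewed, heavy-tailed and zero-spiked distributions in both arms gave 4.8–5.1% for the two-stage rule. Taking the smaller of the two p-values would give 5.7–7.1%.

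**The case against.** The strongest reply is that nothing here is broken. A t-test on change scores is standard and unbiased, the entry cap acts on both arms alike, and a fixed switch holds its error rate. The precision gain rests wholly on assumed inputs, vanishes with a restricted baseline, and shrinks towards 140/70, which is probably nearer the true Month 1 N. All of that stands, and it limits the point to an improvement.

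The Wilcoxon example can be said to overstate the cost, since the SAP plans neither test unconditionally. That is fair: against always using the t-test, the switch costs about 4–5 points of power in that constructed case, or about 7 if each arm is checked separately, not 11.

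On the missing estimate, SAP 5.1 provides arm means and SDs, and Protocol Section 10 allows confidence intervals for means where appropriate. A reader could build the unadjusted difference from these. What remains absent is a planned between-group difference with its interval. The unseen table specifications might define the normality check, so the gap is claimed for the SAP text only; the choice of test belongs in the SAP in any case.

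One qualification cuts the other way. The SAP does not say whether the t-test is pooled or Welch. With equal means but unequal SDs at 112/56, the two-stage rule with a pooled t-test rejected in 2.6% of runs (treatment SD 1.5 times control) or 8.3% (the reverse). Welch stayed near 5% in both cases. The statement that the comparison is valid therefore refers to the null of no treatment effect, with the rule fixed in advance.

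**Conclusion.** The point holds as an improvement, not as the repair of an invalid analysis. The undefined check, the mismatch between a rank test and a mean target, and the missing between-group estimate follow from the text alone. The precision gain is conditional on the assumed SD, correlation and effect: a variance ratio of 0.73–0.93 with baseline limited only by the cap, and 0.94–1.01 with a restricted baseline. In power, for 8 points with a latent baseline mean of 45, that is 12 points at best at 112/56 and 11 at 140/70. With a large true effect the significance conclusion would not change. No bias is shown, and no type I error inflation under no treatment effect. Confidence is medium, because the documents do not allow the gain to be sized.

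**What to change.** In SAP 5.4.2, replace the switch with one prespecified analysis: ANCOVA of Month 1 FACE-Q change on treatment and baseline FACE-Q converted score, with robust standard errors (which also removes the pooled-or-Welch question). Report the adjusted mean difference, 95% CI and p-value. Delete the normality condition and keep the Wilcoxon test as a named sensitivity analysis.

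Add site as a covariate only after two entries are reconciled: Protocol 7.4 says "Randomization will be within each study site", while the tabular summary in Protocol 12.6 lists no stratification factor.

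The cost is SAP wording, with no new data. The change should be made before the randomization schedule is released.

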- The start and end of treatment periods listed above for the mis-treated participants (ie., randomized to Treatment and did not receive Volite or randomized to Control and was treated with Volite prior to the primary timepoint) will be determined based on the treatment received.
- For CP, effectiveness analyses and baseline characteristics will be performed on the mITT population using the “as-randomized” assignment.

JUVÉDERM VOLITE™ XC

- For TP, effectiveness and safety summaries will be performed on the VT population by treatment group.
- For RP, effectiveness and safety summaries will be performed on the VRT population.
- The baseline for applicable effectiveness endpoints and safety parameters will be the last non-missing assessment on or before the latter of randomization date or first treatment date in the control period
- The change from baseline values will be computed as the post-baseline value minus the baseline value.
- Continuous variables will be summarized by number of participants with observed values (n), mean, standard deviation (SD), median, 1st and 3rd quartiles (Q1, Q3), minimum (min), and maximum (max). Categorical variables will be summarized by the number of participants with observed values or events (n), frequency count (N1), and percentage of participants with observed values or events.
- All statistical hypothesis tests will be performed at the 2-sided 5% significance level, unless stated otherwise.
- In general, statistical analyses will be performed using SAS version 9.4 or higher. Adverse events (AEs) and medical history will be coded using the Medical Dictionary for Regulatory Activities (MedDRA) version 22.1 or higher.
- WHO Drug Dictionary will be used to code medications.

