5.3.2. Main Analytical Approach

The missing data in ACSS at Month 1 of CP will be imputed using the Multiple Imputation (MI) method for the mITT population as follows:

Step 1: The missing data will be imputed by cheek side and treatment group using the Fully Conditional Specification (FCS) method with seed = 820403 and nimpute = 30 based on the following model:

$$\text{Month 1 ACSS} = \beta_0 + \beta_1 \times \text{Age} + \beta_2 \times \text{Baseline ACSS}$$

Step 2: After imputation, the changes from baseline will be calculated, from which the responder status in ACSS at Month 1 of CP will be determined.

Step 3: Each complete dataset obtained from Steps 1 and 2 will be analyzed using SAS procedure FREQ

Step 4: The pooled results will be obtained using PROC MIANALYZE

The number and proportion of participants who achieved at least 1-point improvement from baseline at Month 1 of CP will be tabulated by treatment group. The aggregated responder rates by treatment group and the associated p-value and 95% CI estimated based on the normal approximation to assess the difference in the ACSS responder rate at Month 1 of CP between JUVÉDERM VOLITE XC and the no-treatment control will be presented. If the 2-sided p-value is less than 0.05, then the ACSS responder rate at Month 1 in JUVÉDERM VOLITE XC is statistically significantly different from that in the no-treatment control group during the control period. Furthermore, if the responder rate is greater for JUVÉDERM VOLITE XC than the no-treatment control group, then VOLITE will be considered superior to the no-treatment control group.

The detailed SAS codes are as follows:

```
proc mi data=adeff seed=820403 nimpute=30 out=mi;
  by trt01p cheek;
  class acss0 acss1;
  fcs logistic(/details);
  var age acss0 acss1;
run;
data lmi rmi; *separate imputed datasets by cheek side;
  set mi;
  if cheek='Left' then output lmi;
  if cheek='Right' then output rmi;
run;
data all; *obtain responder status variable;
  merge lmi rmi;
```

JUVÉDERM VOLITE™ XC

```
by _imputation_ subjid;
ldiff=lacss0-lacss1;
rdiff=racss0-racss1;
resp=0;
if ldiff >= 1 and rdiff>=1 then resp=1;
run;
ods output RiskDiffCol2=risk(where=(index(row,'Total')=0));
proc freq data=all;
  by _imputation_;
  tables trt01p*resp/riskdiff;
run;
proc sort data=risk; by row;
ods output VarianceInfo=Variance1;
ods output ParameterEstimates=Param1;
proc mianalyze data=risk;
  by row;
  modeleffects risk;
  stderr ase;
run;
```

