5.3.3. Sensitivity Analyses

Two sensitivity analyses of the primary effectiveness endpoint, the ACSS responder status at Month 1 in CP based on EI's assessment, will be performed as follows:

- A tipping point analysis using the mITT population will be conducted to evaluate all possible combinations of participants with missing Month 1 ACSS assessments counted as responders in both treatment groups. A diagram of 2-sided p-values based on the Fisher's exact test with the x-axis and y-axis displaying the number of imputed responders out of the total number of participants with missing Month 1 ACSS assessment in VOLITE and Control group, respectively and the p-values ≤ 0.05 and >0.05 in different colors will be presented.
- The ACSS responder at Month 1 of CP will be analyzed using the Observed Primary Endpoint population. The number and proportion of participants of ACSS responder will be tabulated by treatment group. The between-group difference in the responder rate, 95% CI for the responder rate difference, and p-value based on the Fisher's exact test will be presented.

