5.5. Other Effectiveness Endpoints Analysis

The other effectiveness endpoints listed in [Table 5-4](#) will be summarized descriptively based on the observed data.

The analyses of CP will be performed for the mITT population at Baseline and Month 1. The analyses of TP will be performed for the VT population at Baseline and Months 1, 2, 4, and 6.

JUVÉDERM VOLITE™ XC

The analyses of RP will be performed for the VRT population at Baseline and Months 1 and 4 post the repeat treatment.

The composite responder status is defined based on ACSS and FACE-Q Satisfaction with Skin Questionnaire overall converted score. A participant is counted as a composite responder if both criteria listed below are met:

- ACSS criterion: A participant with at least 1-point reduction from baseline in ACSS on both cheeks will be considered as an ACSS responder
- FACE-Q satisfaction with skin responder: A participant with change from baseline in FACE-Q overall converted score \geq half of standard deviation of FACE-Q overall converted score at baseline ([Pusic 2013](#))

Table 5-4 **Other Effectiveness Analyses**

Endpoint	Description	Analysis Period	Methodology
ACSS responder status as assessed by EI	Number (%) of responders by treatment group	TP, RP	Frequency counts and percentages
Raw value and change from baseline in ACSS	Summary by treatment group	CP, TP, RP	Continuous descriptive statistics
Raw value and change from baseline in FACE-Q Satisfaction with Skin questionnaire overall converted score	Summary by treatment group	TP, RP	Continuous descriptive statistics
Item score of FACE-Q Satisfaction with Skin questionnaire and aggregated categories of “satisfied” and “dissatisfied”	Number (%) of each response category by treatment for each of 12 individual items	CP, TP, RP	Frequency counts and percentages
AFLS responder status as assessed by EI	Number (%) of responders by treatment group	TP, RP	Frequency counts and percentages
Raw value and change from baseline in AFLS	Summary by treatment group	CP, TP, RP	Continuous descriptive statistics
Raw value and change from baseline in FACE-Q Appraisal of Lines questionnaire overall converted score (see Section 6.5.3 and Section 6.5.4)	Summary by treatment group	CP, TP, RP	Continuous descriptive statistics

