5.7. Other Analyses

5.7.1. Subgroup Analyses

Analysis of the primary effectiveness endpoint, ACSS responder status at Month 1, will be performed separately by the following subgroups based on the observed data:

- Baseline ACSS score: 2 and 3
- Fitzpatrick skin phototype: I/II, III/IV, and V/VI

JUVÉDERM VOLITE™ XC

- Volume injected: \leq median and $>$ median
- Injection plane/technique: microdepot intradermal injection vs. other injections
- Investigational site

The median total volume injected for the initial and touch-up treatments combined on both cheeks will be calculated to determine the cut-off for the subgroup listed above. Participants who received microdepot non-intradermal injections, non-microdepot intradermal, or non-microdepot non-intradermal injections for the initial or touch-up treatment are included in the subgroup of “other” injections.

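### Does the SAP's silence on missing Month 1 AFLS scores leave this secondary endpoint undetermined?

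*SAP*

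**What the plan says.** SAP 5.4.2 gives, for AFLS, a confidence interval for each group's responder rate and a Fisher comparison "using the mITT population with baseline AFLS score of 2 on both cheeks or 3 on both cheeks". The mITT definition in SAP Table 4-1 requires a baseline ACSS score on both cheeks and no Month 1 AFLS score, so membership alone does not settle who is in the denominator.

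Elsewhere the SAP does state its handling of missing data:

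- **ACSS, primary (5.3.2):** "The missing data in ACSS at Month 1 of CP will be imputed using the Multiple Imputation (MI) method for the mITT population".
- **ACSS, sensitivity (5.3.3):** "The ACSS responder at Month 1 of CP will be analyzed using the Observed Primary Endpoint population", plus a tipping-point analysis.
- **FACE-Q (5.4.1):** "The analysis will be conducted using observed data (eg, no imputation for missing baseline or Month 1 FACE-Q scale scores".
- **Other endpoints (5.5):** these "will be summarized descriptively based on the observed data".
- **Subgroups (5.7.1):** the analysis "will be performed separately by the following subgroups based on the observed data".
- **General convention (5.1):** "Categorical variables will be summarized by the number of participants with observed values or events (n", with percentages on the same basis.

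Protocol 10.3 leaves missing-data procedures to the SAP. Protocol 10.3.1.2 counts missing Month 1 data as non-response for the primary analysis and refers to the SAP for details. Protocol 10.3.1.3 says the AFLS rate is analyzed like the ACSS rate.

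**The concern.** AFLS is one of two secondary endpoints, and it is the only inferential effectiveness analysis with no missing-data sentence of its own. Three rules can be argued for. The protocol's link from AFLS to ACSS, followed back to the protocol's ACSS rule, gives non-response. The same link followed to the SAP's ACSS rule gives multiple imputation. The SAP's general convention gives observed cases. There is also a programming route to non-response. The ACSS code starts every participant at zero and then applies "if ldiff >= 1 and rdiff>=1 then resp=1". SAS ranks a missing value below any number, so the same code run on unimputed AFLS data would turn a missing score into a non-response without anyone deciding it.

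The rules part company when loss differs between arms, and the design allows for that. Month 1 is counted from the last treatment in the treated arm, so a participant with a touch-up reaches it about 60 days after randomization, while controls reach it at about 30 days. Non-response costs power if more treated participants are lost, and inflates false positives if more controls are lost. Neither sensitivity analysis in SAP 5.3.3 covers AFLS.

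**Working it through.** **1. The plan's own figure.** Inputs from SAP section 3 and Protocol 10.1: 72 treated and 36 control, 80% against 45%, two-sided Fisher test at 5%. Power is the sum over all pairs (a, b) of Bin(a; 72, 0.80) × Bin(b; 36, 0.45), counting pairs with p < 0.05 and the treated rate higher. Result: 0.9440, which is the stated 94.4%.

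**2. Which rule that figure assumes.** At least 135 eligible participants at 2:1 gives 90 and 45. Less 20%: 90 × 0.80 = 72 and 45 × 0.80 = 36. The lost participants are removed from the denominators, as in an observed-case analysis. Under non-response the denominators would stay at 90 and 45.

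**3. The text side by side.**

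| Reading for AFLS | For | Against |
|---|---|---|
| Observed cases | General convention in SAP 5.1; no imputation step; ordinary Fisher test; 72/36 | Not stated in 5.4.2 |
| Multiple imputation | Protocol link to ACSS | SAP 5.3.2 text, model and code cover ACSS only and pool by normal approximation, not Fisher |
| Non-response | Protocol link to ACSS | Protocol rule is for the primary analysis, defers to the SAP, and the SAP replaced it even there |

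The responder code in 5.3.2 runs after imputation, on complete ACSS data. Nothing tells a programmer to apply it to unimputed AFLS scores.

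**4. Size if non-response were used anyway.** Assumptions: 90/45 eligible, 80% against 45% among those observed, missingness unrelated to response, a binomial number missing in each arm. Both rules are applied to the same data.

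The documents give no Month 1 loss. One scenario can be built from the touch-up mechanism: equal monthly loss m, with 23.7% of treated participants needing a second month (V12-001, Protocol 3.2). Treated loss = 1 − [0.763(1 − m) + 0.237(1 − m)²].

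- m = 5%: 1 − (0.7249 + 0.2139) = 6.1%.
- m = 10%: 1 − (0.6867 + 0.1920) = 12.1%.

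| Loss, treated/control | Power, observed cases | Power, non-response | Rules disagree |
|---|---|---|---|
| 5%/5% | 97.4% | 95.9% | 2.2% |
| 6.1%/5% | 97.3% | 94.8% | 3.0% |
| 10%/10% | 96.6% | 93.4% | 4.3% |
| 12.1%/10% | 96.5% | 90.4% | 6.7% |
| 20%/20% | 94.4% | 86.4% | 9.9% |
| 20%/10% | 95.9% | 72.1% | 23.9% |

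At 6.1%/5% the gap is 97.3 − 94.8 = 2.5 points, and both values are above the stated 94.4%.

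**5. False positives.** With 45% in both arms, a significant result favoring treatment occurs in 1.9% of trials with observed cases and 1.8% with non-response at 6.1%/5%. At 12.1%/10% the figures are 1.9% and 1.5%. All are below the nominal one-sided 2.5%. Inflation (6.0% under non-response at 5%/15%) needs controls to be lost more often, the reverse of the touch-up mechanism.

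**The case for a change.** The best case for a change is that an unstated rule on a secondary endpoint of a pivotal study can be chosen after the results are seen. The SAP defines a separate observed population for ACSS but none for AFLS, and its observed-data sentence in 5.4.1 sits in the FACE-Q paragraph. It is also possible to build data where the rule decides the result. With 9 treated and 2 control participants missing, 54/81 against 20/43 gives p = 0.035, while the same data as 54/90 against 20/45 give p = 0.10.

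Part of this stands. Section 5.4.2 has no sentence on the point, the FACE-Q sentence should not be stretched to cover AFLS, and the arithmetic is right. But the example has an observed difference of about 20 points (66.7% against 46.5%), not the planned 35, so it lies near the threshold under either rule. The heavy-loss rows borrow 20% from attrition over the whole study. Month 1 loss should be smaller: the analysis windows are wide (Day 2 to Day 46 after last treatment; for controls, Day 2 to optional treatment or exit), and controls are offered treatment only after completing the control month. An AFLS sensitivity analysis would be a reasonable extra, but study success rests on ACSS and the plan is not unsound without it.

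**Conclusion.** No change follows. This is a gap that an analyst fills sensibly from the rest of the SAP: include the participants in the AFLS subset who have Month 1 scores on both cheeks, and do not impute. That reading agrees with the general convention, the named test and the sample size, and it delivers the stated 94.4% at 72/36. No stated rule has been shown to be wrong. A sentence in 5.4.2 would only record what the SAP already implies.

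Should someone use non-response instead, the cost in the touch-up scenario is about 2.5 points of power (6.1%/5% loss) or 96.5 − 90.4 = 6.1 points (12.1%/10%), with no inflation of false positives. These sizes rest on assumed Month 1 loss, missingness unrelated to response, the 80% and 45% rates holding among those observed, and the V12-001 touch-up rate carrying over. Multiple imputation was not simulated. Under the same missingness assumption its responder rates should lie close to the observed-case rates. Much heavier or more unequal loss at Month 1 would make the choice matter more, but the documents give no reason to expect it.
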